5.10 List of Variables

Demographic Variables

Variables	Type	Value	Expression
Age	Discrete	In completed years	Mean \pm SD
Sex	Categorical	Male / Female	Frequency (%)
Monthly income	Continuous	In local currency (BDT)	Mean \pm SD /Median (IQR)

Clinical Variables

Variables	Type	Value	Expression
Duration of diabetes	Discrete	In years	Mean \pm SD
Duration of HTN	Discrete	In years	Mean \pm SD
Current medication for DM	Categorical	Insulin/Oral Hypoglycemic Agents/Both	Frequency (%)
Current medication for HTN	Categorical	ACE inhibitor/ARB/MRAs/Beta-blocker/Calcium channel blocker/Diuretics/Others	Frequency (%)
Blood pressure	Continuous	In mm Hg	Mean \pm SD
Height	Continuous	Meter	Mean \pm SD
Weight	Continuous	Kg	Mean \pm SD
BMI	Continuous	kg/m ²	Mean \pm SD
Adverse events	Categorical	Present / Absent	Frequency (%)

Biochemical Variables

Variables		Type	Value	Expression
UACR		Continuous	mg/g	Mean \pm SD
eGFR		Continuous	mL/min/1.73 m ²	Mean \pm SD
Serum creatinine		Continuous	mg/dL	Mean \pm SD
Serum potassium		Continuous	mmol/L	Mean \pm SD
Fasting blood glucose		Continuous	mg/dL	Mean \pm SD
2 hour postprandial blood glucose		Continuous	mg/dL	Mean \pm SD
HbA1C		Continuous	Percent (%)	Mean \pm SD
Urinalysis	Albumin	Categorical	-/trace/+/++/+++/++++	Frequency (%)
	RBC	Discrete /HPF	Mean \pm SD
	WBC	Discrete /HPF	Mean \pm SD

5.11 . Operational definitions:

A. CKD : According to 2024 KDIGO guideline for CKD , CKD is defined as abnormalities of kidney structure or function, present for a minimum of 3 months, with implications for health . Criteria for chronic kidney disease (either of the following present for a minimum of 3 months)

1. Markers of kidney damage (1 or more):

- a. Albuminuria ($\text{ACR} \geq 30 \text{ mg/g}$ [$\geq 3 \text{ mg/mmol}$])
- b. Urine sediment abnormalities
- c. Persistent hematuria
- d. Electrolyte and other abnormalities due to tubular disorders
- e. Abnormalities detected by histology
- f. Structural abnormalities detected by imaging
- g. History of kidney transplantation

2 . Decreased GFR : $\text{GFR} < 60 \text{ ml/min per } 1.73 \text{ m}^2$ (GFR categories G3a-G5)

B. Diabetes Mellitus: Previously diagnosed Diabetic patients on insulin or oral antidiabetic drug or those having Fasting blood glucose $\geq 7 \text{ mmol/l}$ (126 mg/dl) or Postprandial glucose $\geq 11.1 \text{ mmol/l}$ (200 mg/dl) during OGTT or HbA1C $\geq 6.5\%$.(ADA, 2010)

C. eGFR: The CKD-EPI equation, expressed as a single equation, is:

- $\text{GFR} = 141 \times \min(\text{Scr}/\kappa, 1)^\alpha \times \max(\text{Scr}/\kappa, 1)^{-1.209} \times 0.993^{\text{Age}} \times 1.018$ [if female] $\times 1.159$ [if black]

Scr is serum creatinine (mg/dL), κ is 0.7 for females and 0.9 for males, α is -0.329 for females and -0.411 for males, min indicates the minimum of Scr/ κ or 1, and max indicates the maximum of Scr/ κ or 1.

D. Diabetic Nephropathy: Diabetic patients with urinary albumin excretion >30 mg/g on at least two occasions three months apart and no other kidney or renal tract disease.(Tuttle et al., 2014)

E. Genital and perineal hygiene : Patient education about genital and perineal hygiene should be taken as a preemptive measure for all the diabetic patients irrespective of the antidiabetic therapy. This should include washing of genital organs followed by urination or defecation, routine hygienic wipes or sprays, women should be advised to wash from front-to-back, uncircumcised males should retract the prepuce before wash, use clean water for washing or mild soap if required, alcohol-based disinfectant should not be used for washing.(Unnikrishnan et al., 2018)

F. Withdrawal criteria

1. A sustained decrease in eGFR to <15 mL/min/1.73 m² or sustained decrease in eGFR \geq 40% compared to baseline over \geq 4 weeks was defined by evidence of \geq 2 consecutive laboratory assessments or need to start dialysis (Bakris et al., 2020)
2. Persistently high potassium level \geq 5.5 mmol/l even after holding Finerenone for 3 days and adjusting other diet and medications.
3. If patient develops diabetic ketoacidosis (DKA) including euglycemic DKA. DKA will be defined as blood glucose >11.1 mmol/L, urine ketone bodies more than 2+ on dipstick testing and a serum bicarbonate level <15 mmol/L.
4. If patient develops symptoms and signs suggestive of Fournier's gangrene (pain, swelling, erythema, foul-smelling discharge or necrosis) in the perineal or genital area.
5. Drug intolerance or patient refusal to continue medication due to adverse effects like dizziness, arthralgia etc.
6. The patient wants to withdraw himself from the study
7. If any participant becomes pregnant during the study period

G. Adverse Events: (AE)

An AE is defined as any untoward medical occurrence in a clinical trial patient during the study; the event does not necessarily have a causal relationship with that treatment. Therefore, an AE can be any unfavorable and unintended sign (including any clinically significant abnormal laboratory finding), symptoms, or disease, temporally associated with using a medicinal product. The most common adverse event of finerenone is hyperkalemia. Other common adverse events are decreased GFR, hypotension, back pain, dizziness, arthralgias, constipation. The most common adverse events of dapagliflozin is genital mycotic infection. Other adverse events are urinary tract infection, hypotension, hypoglycemia, acute kidney injury, DKA, Fournier's gangrene.

Major adverse events will be defined as any event leading to admission or prolonged admission, withdrawal, or death.

Minor adverse events will be defined as minor if it does not require admission to the hospital or withdrawal of the drug.

Drug intolerance refers to the inability to tolerate the adverse effects of medication at a therapeutic or substantial dose.

H. Treatment Compliance :Compliance to study treatment, calculated as ([overall amount of dose actually taken] / [overall expected amount of dose to be taken]) × 100%, was also assessed (on-treatment + 7 days analysis set, *i.e.*, all patients who received one dose of study treatment and censored at 7 days after treatment discontinuation). The dose taken was based on medication returned by patients to their clinics. Adequate treatment compliance was defined as $\geq 75\%$, and significant noncompliance was defined as $< 50\%$. (Carolina, 2023)

5.12 Data collection instrument: A structured pretested case record form.

5.13 Data collection procedure:

Baseline evaluation: Patients with chronic kidney disease and type 2 diabetes will be screened consecutively and prospectively by the above inclusion and exclusion criteria to select eligible patients. Eligible patients and their legal relatives will be fully explained the study protocol, their role in the study, and the risk of the study. They will be enrolled in the study after getting written informed consent. Demographic and clinical information will be collected as per the case record form by interviewing the patients, reviewing the medical records, and performing physical examinations. After taking proper history and physical examinations, blood and urine samples will be collected for biochemical analysis. Blood tests will include measurement of Serum Creatinine, Estimated Glomerular Filtration Rate (eGFR), Serum Potassium, Fasting Blood Sugar (FBS), 2-Hour Postprandial Blood Sugar (2HPPBS) and HbA1C. Urine samples will be analyzed for Urine Albumin-Creatinine Ratio (first morning urine) and routine examination (R/E), including albumin, RBC and WBC. If a patient reports symptoms or any biochemical findings suggestive of a Urinary Tract Infection (UTI), a urine culture and sensitivity (C/S) test will be performed. Baseline clinical and laboratory parameters will be recorded in the case record form.

Randomization: Once a participant is enrolled in the study and consents to participate, they will be assigned to a treatment group according to the randomization sequence. Patients will be randomly assigned to either experimental groups or control group with a 1:1 ratio (block size of four). Randomization will be carried out using online software (Research Randomizer Version 4.0 at <https://www.randomizer.org>).

Blinding: The study will be open-label, with both participant and the researcher aware of their treatment allocation.

Treatments: The treatment phase lasted for eight weeks. The experimental group will receive oral dapagliflozin 10 mg plus Finerenone 10 mg daily. While the control group will receive oral dapagliflozin 10 mg daily. All the patients will be advised to follow standard dietary advice (including low salt <5gm/daily, diabetic diet), regular exercise, regular home capillary glucose monitoring & maintain all the standard pharmacological therapies throughout the study, including oral antidiabetic drug/insulin and any other antihypertensive medications (if required).

Evaluation of patients at 4 weeks: The patients will be followed up at 4 weeks. The physical examinations will be done, and the following parameters will be measured at follow-up: Serum creatinine, eGFR, serum potassium, FBS, 2HPPBS, Urine R/E and Urinary ACR. The patients will be instructed to report immediately in case of any adverse events following consumption of the drugs. If a patient develops symptoms or signs suggestive of genital mycotic infection (itching, erythema, discharge), a culture and sensitivity (C/S) test of vaginal discharge (in female) or penile swab (in male) will be performed. Tolerability will be assessed by employing an adverse event profile (adverse events, serious adverse events). Safety will be evaluated based on the incidence of A/E. The safety population consists of subjects who receive at least one dose of study medication. Necessary action will be taken for any adverse effect complained by participants.

Evaluation of patients at 8 weeks and outcome assessment: All the patients will be evaluated at 8 weeks again. Physical examination will be done. Biochemical parameters will be reassessed, including Serum Creatinine, eGFR, Serum Potassium, FBS, 2HPPBS, urine R/E and urinary ACR. If a patient does not return for a scheduled visit, every effort will be made to contact the patient. If possible, every effort will be made to document patient outcomes in any circumstance. The investigator will enquire about the reason for withdrawal, request that the patient return all unused study medication, and ask that the patient return for a final visit, if applicable, and follow up with the patient regarding any unresolved adverse events

In every visit, for blood test, blood will be collected from accessible vein with proper aseptic precaution and patient remained at least 8 hours overnight fasting before blood collection and blood was collected into red topped vacutainer. After collection of 10 mL blood, it will be allowed to clot by leaving it undisturbed at room temperature for 10-15 minutes and will removed the clot by centrifuging at 3000rpm for 10 minutes for serum. Serum creatinine concentration will be measured by buffer kinetic jaffe reaction using a SIEMENS dimension EXL200 analyzer while eGFR will be measured by CKD-EPI formula. The urinary albumin concentration was determined using a nephelometry method by BN pro-spec analyzer while urinary creatinine concentration was measured by endpoint spectrophotometric method with an alkaline picrate solution using a SIEMENS dimension EXL200 analyzer. UACR will be calculated by dividing the concentration of urinary albumin by the concentration of urinary creatinine. All the investigations will be performed in an ISO certified laboratory.

5.14. Data analysis:

Data will be recorded in the form of an Excel worksheet. After completion of data collection, data will be analyzed using the Statistical Package for Social Sciences (SPSS) version 27.0 (IBM Corp., Armonk, NY, USA). The continuous variables will be presented by measures of central tendency and measures of dispersion. For the normally distributed data, mean \pm standard deviation will be used, and for non-parametric data, median and Interquartile range (IQR) will be presented. On the other hand, we would present the categorical variables as frequency distribution. Between groups, comparisons of independent variables will be performed by independent t-test and Mann-Whitney U-test for normally and not-normally distributed variables respectively. Within patients, comparison will be performed by paired t-test or Wilcoxon Signed Rank Test, as appropriate. The Chi-square test will investigate the differences in categorical variables between two groups. Repeated measures ANOVA will be performed to compare mean values across multiple time points within the same group. Where appropriate, post-hoc analysis with Bonferroni correction will be conducted to identify specific time points with significant difference. A p-value <0.05 will be considered statistically significant.

[figure not shown]
5.15. The utilization of results: This trial will provide critical evidence on the efficacy and safety of dapagliflozin-finenone combination in a resource-limited setting, addressing a significant unmet need in the management of DN. Every effort will be made to publish the results in peer-reviewed national and international journals. The results of this study will be published as a thesis and submitted to the corresponding university as MD (Nephrology) exam requirement. The result of the study will be presented to the Department of Nephrology, CMCH.

5.16. Ethical Implication: The study will be conducted after the approval of the Ethical Review Committee of Chittagong Medical College. Voluntary written consent will be taken from the patient and legal guardians. All measures will be taken to protect anonymity. The interviews of the patient, clinical examination and investigations will be performed at the respective hospital after explaining the nature and purpose of the study to them, assuring that the information given by them will be used for the interest of the community and that the particulars of the patients will not be disclosed anyway.

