To evaluate the effect of dapagliflozin-finerenone combination on albuminuria in patients with chronic kidney disease and type 2 diabetes compared to dapagliflozin alone.

4.2 Specific Objectives:

1. To compare the change in urinary albumin-to-creatinine ratio (UACR) from baseline to the end of the study between dapagliflozin - finerenone combination group and dapagliflozin alone group.
2. To compare the changes in serum potassium levels between the two groups during the study period.
3. To estimate and compare the changes of eGFR between the two groups.
4. To evaluate the proportion of patients achieving a clinically significant reduction in albuminuria (e.g., $\geq 30\%$ decrease in UACR) in each groups.
5. To evaluate the overall safety and tolerability profiles of the combination therapy compared to dapagliflozin monotherapy.

5. Materials and method:

5.1. Type of study: Randomized, open-label, active controlled trial.

5.2 Place of Study: Department of Nephrology, Medicine and Endocrinology & Metabolism, Chittagong Medical College Hospital, Chattogram, Bangladesh.

5.3 Study period: One and half year from acceptance of protocol.

5.4 Study population: Adults with chronic kidney disease and type 2 diabetes attending the Nephrology, Medicine and Endocrinology & Metabolism outdoors at CMCH will be the study population during the study period.

5.5 Study groups: Based on the interventions, there will be two groups in the study

1. Experimental group: Dapagliflozin 10 mg plus finerenone 10 mg
2. Control group : Dapagliflozin 10 mg alone

5.6 Sampling technique: Consecutive patients attending the Nephrology, Medicine and Endocrinology & Metabolism Departments at CMCH will undergo screening based on predefined inclusion and exclusion criteria. Eligible participants will be randomly allocated (via computer-generated randomization) to one of the two treatment arms.

5.7 Inclusion criteria:

- Patients aged ≥ 18 years
- Patients with T2 DM , as defined by the American Diabetic Association.
- Urinary ACR ≥ 30 mg/g and eGFR ≥ 25 ml/min per 1.73 m²
- Prior treatment with ACEIs or ARBs for more than four weeks up to the maximum tolerated dose
- Serum potassium ≤ 4.8 mmol/L

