5.8 Exclusion criteria

- Patients with other known causes of proteinuria, e.g. UTI, fever
- At screening visit SBP higher than 160 mmHg or DBP higher than 100 mmHg or SBP lower than 90 mmHg
- Glycated hemoglobin (HbA1C) >11%
- Known hypersensitivity to dapagliflozin or finerenone
- Known case of Addison's disease
- Known case of hepatic insufficiency
- Treatment with SGLT2i (empagliflozin:62 hours, dapagliflozin:65hours) or MRAs (finerenone:10-20 hours, spironolactone:7 hours , eplerenone:15-30 hours) within their wash out periods.
- Patients on non-dihydropyridine Calcium Channel blockers or Glucagon-like peptide-1 (GLP-1) agonists
- Pregnant lady or lactating mother

5.9. Sample size: Sample size calculation for hypothesis testing of difference between two proportions:

$$n = \frac{p(100 - p) + q(100 - q)}{(p - q)^2} (z_{\alpha} + z_{\beta})^2$$

Where,

Z_{α} = Z value of standard normal distribution at a definite level of significance

Z_{β} = Z value of standard normal distribution at a definite level of power

p = Percent change from baseline in UACR after treatment in the experimental group

q = Percent change from baseline in UACR after treatment in the control group

Here,

Z_{α} = 1.96 at 95% Confidence Interval

Z_{β} = 1.28 at 90% power

p = 36% (Mårup et al., 2024)

q = 8% (Mårup et al., 2024)

So,

$$n = \frac{36(100-36) + 8(100-8)}{(36-8)^2} (1.96 + 1.28)^2 \approx 40$$

Considering 10% lost to follow-up final sample will be $(40 + 40 \times 10\%) = 44$. That means 44 patients in each group will be needed to test the hypothesis.

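### Pregnancy is both an exclusion and a withdrawal criterion, but no pregnancy test is listed at any visit, so an early unrecognised pregnancy could be randomised and dosed

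*Protocol*

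**What the plan says.** **Eligibility.** Section 5.7 admits "Patients aged ≥ 18 years" and sets no condition on menopausal status, childbearing potential or contraception. Section 5.8 excludes a "Pregnant lady or lactating mother".

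**Withdrawal.** Section 5.11 F, item 7 applies "If any participant becomes pregnant during the study period". Neither rule says how pregnancy is to be ascertained.

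**Baseline (5.13).** The order of work is: "After taking proper history and physical examinations, blood and urine samples will be collected for biochemical analysis". The blood tests named are creatinine, eGFR, potassium, fasting and two-hour glucose, and HbA1C. For urine: "Urine samples will be analyzed for Urine Albumin-Creatinine Ratio (first morning urine) and routine examination (R/E), including albumin, RBC and WBC". A urine culture is added if infection is suspected. Assignment to a group follows enrolment and consent.

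**Week 4 (5.13).** Physical examination, then "Serum creatinine, eGFR, serum potassium, FBS, 2HPPBS, Urine R/E and Urinary ACR".

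**Week 8 (5.13).** Physical examination, then: "Biochemical parameters will be reassessed, including Serum Creatinine, eGFR, Serum Potassium, FBS, 2HPPBS, urine R/E and urinary ACR".

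**Case record form (Appendix).** The form has 14 biochemical rows, including tests done only on suspicion (urine culture, genital swab, urine ketones, serum bicarbonate), and 12 adverse-effect rows. None concerns pregnancy.

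**The concern.** The sponsor has already decided that pregnancy is incompatible with being in this trial, both at entry and during treatment. The question is whether the procedures can put that decision into effect. A woman who knows she is pregnant can say so, and an advanced pregnancy would be seen on examination. An early pregnancy that she does not know about would be found only by a test, and none is listed.

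At stake is avoidable exposure to study drug in someone the protocol's own safety rule is meant to keep out or take off treatment. Treatment lasts eight weeks, which is the outer limit of such exposure and not an estimate of risk. Week 4 is the only scheduled visit during treatment at which dosing could still be stopped, and the list for that visit has no pregnancy test.

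**Working it through.** The point concerns a missing procedure. The check is therefore a count of what each visit requires, set against the two pregnancy rules.

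**1. Tests itemised in 5.13**

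| Visit | Blood | Urine | Total | Pregnancy tests |
|---|---|---|---|---|
| Baseline | 6 (creatinine, eGFR, potassium, FBS, 2HPPBS, HbA1C) | 2 (UACR, routine examination) | 8 | 0 |
| Week 4 | 5 (as baseline, without HbA1C) | 2 | 7 | 0 |
| Week 8 | 5 | 2 | 7 | 0 |
| All | 16 | 6 | 22 | 0 |

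eGFR is calculated from creatinine. If it is not counted as a separate test, the totals are 7 + 6 + 6 = 19. The number of pregnancy tests is zero either way.

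**2. Case record form.** There are 14 biochemical rows and 12 adverse-effect rows, with none for pregnancy. This is supporting evidence only, because the form also has no row for several other exclusions.

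**3. Withdrawal criteria that rest on a laboratory result, against the form**

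| Criterion in 5.11 F | Measurement on the form |
|---|---|
| 1. Sustained fall in eGFR | Creatinine and eGFR |
| 2. Persistent high potassium | Serum potassium |
| 3. Ketoacidosis | Glucose; urine ketones and bicarbonate if suspected |
| 7. Pregnancy | None |

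Pregnancy is the one criterion that a laboratory test could detect but that has no measurement behind it.

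**4. What is left to detect pregnancy.** At baseline there is interview, record review and physical examination. At weeks 4 and 8 there is physical examination. These can pick up a known or evident pregnancy but not an early unrecognised one.

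**5. How many women.** The documents give no sex split, age distribution or pregnancy rate, so no expected number can be calculated.

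**The case against.** The strongest reply is that this is an omission and not a contradiction. Sections 5.8 and 5.11 F agree with each other and nothing in 5.13 conflicts with them. Section 5.13 first screens patients against the eligibility criteria by interview, records and examination. Its list of tests closely follows the biochemical variables in 5.10, so it may be a data-collection list and not a full account of how each exclusion is verified. The baseline blood list is also worded as inclusive. All of this is fair. But a test that is not listed is not required and may be done inconsistently, and following the listed procedures to the letter still lets an unrecognised pregnancy through.

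Four further points:

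- **Wording of the exclusion.** Some exclusions are limited to known cases, for example "Known case of hepatic insufficiency", and the pregnancy exclusion is not. Little can be built on this contrast. Lactation, in the same item, is established by asking, and the drug exclusions also lack the word and are checked by history. The finding does not depend on it.
- **Unseen material.** The consent pages and the flow chart (5.18) were not available, and a test could be mentioned there. This stands, and the finding is limited accordingly.
- **Frequency.** Patients must already have had more than four weeks of an ACE inhibitor or ARB, so they are under medical care, and the number affected is probably small. That is a reasonable assumption, but the documents give nothing to test it against.
- **Recording.** A pregnancy could be entered under other adverse effects, as a withdrawal, or as a withdrawal reason in the monitoring board's table. These entries record a pregnancy once found; they do not find it.

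**Conclusion.** The concern holds. The protocol sets two pregnancy rules, and the visits itemised in 5.13 and the case record form contain no test to apply either: 0 of 22 itemised tests over three visits. Followed as written, they could let an early unrecognised pregnancy be randomised and dosed.

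The change should be made, with medium confidence. The number of participants affected is unknown and may be zero. Sample size, power and the UACR comparison are unaffected. The conclusion assumes that no pregnancy test is specified only in the consent pages or the flow chart.

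**What to change.** In 5.13, require a urine pregnancy test, on the urine already collected, for every woman of childbearing potential (for example, not postmenopausal and not surgically sterile). Do it routinely, before randomisation and again at week 4, and not only on suspicion. A confirmed positive leads to exclusion under 5.8 at baseline, or to stopping study drug and withdrawal under 5.11 F, item 7 at week 4. Add one row to the case record form for the result at both visits, marked as applying to women of childbearing potential. If only one test is accepted, the one before randomisation matters most, because it enforces the entry exclusion.

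**Cost.** One protocol line and one form row, with no new visit or sample. Strips for randomised participants:

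| Share of the 88 who are women of childbearing potential (assumed) | Women | Strips (2 each) |
|---|---|---|
| 25% | 22 | 44 |
| 50% | 44 | 88 |
| 100% (ceiling) | 88 | 176 |

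The strip price is not in the documents. Each 10 BDT of price costs at most 176 × 10 = 1,760 BDT, which is 1,760 / 300,000 = 0.59% of the investigation budget line. Repeat tests after a positive, and tests in women who are screened but not randomised, come on top. The protocol gives no screening numbers, so that extra cannot be bounded. The other downside is an occasional false positive that delays entry or interrupts treatment until it is checked.

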Appendix

Case record form

Protocol Title: Effect of dapagliflozin compared to dapagliflozin-finenone combination on albuminuria in patients with chronic kidney disease and type 2 diabetes: A randomized controlled trial.

Patient's identification			
1	Patient ID No.		
2	Name of the patient		
3	Contact no:		
4	Address:		
5	Study group: Group 1: Experimental group Group 2: Control group		
Demographic characteristics			
1	Age:years	
2	Sex:	0=Female 1=Male	
3	Place of residence	1=Urban, 0= Rural	
3	Monthly incomeBDT	
Clinical Characteristics			
1	Duration of Diabetes Mellitus years	
2	Duration of Hypertension years	
3	Current medication for DM	1=Insulin 2=Oral Hypoglycemic Agents 3=Both Insulin and Oral Hypoglycemic Agents	
4	Current medication for HTN	1=ACEi, 2=ARB, 3=MRA, 4=Beta blocker, 5=CCB, 6=Diuretics, 7=Others	
Clinical Parameters		Baseline	4 Weeks
1	Height (cm)		
2	Weight (kg)		
3	BMI (kg/m ²)		
4	Systolic BP (mmHg)		
5	Diastolic BP (mmHg)		
Biochemical Parameters		Baseline	4 Weeks
1	Serum Creatinine (mg/dL)		
2	eGFR (mL/min/1.73m ²)		
3	Serum Potassium (mmol/L)		
4	Fasting Blood Sugar (mg/dL)		
5	2-hour Postprandial Blood Sugar (mg/dL)		
6	Urine Albumin-Creatinine Ratio (UACR) (mg/g)		

7	Urine R/E – Albumin:			
8	Urine R/E – RBC:			
9	Urine R/E – WBC:			
	Biochemical Parameters	Baseline	4 Weeks	8 Weeks
10	HbA1C (%)		-	-
11	Urine Culture & Sensitivity (if UTI suspected):			
12	Vaginal discharge/penile swab for C/S (if genital mycotic infection suspected)	-		
13	Urine for ketone bodies (if DKA suspected)			
14	Serum bicarbonate (if DKA suspected)			

Adverse Effect			4 Weeks	8 Weeks
1	Hyperkalemia	1=Yes 2=No		
2	Hypotension	1=Yes 2=No		
3	UTI	1=Yes 2=No		
4	Genital Mycotic Infection	1=Yes 2=No		
5	Hypoglycemia	1=Yes 2=No		
6	Dizziness	1=Yes 2=No		
7	Constipation	1=Yes 2=No		
8	Acute Kidney Injury (AKI)	1=Yes 2=No		
9	Diabetic Ketoacidosis (DKA)	1=Yes 2=No		
10	Fournier's gangrene	1=Yes 2=No		
11	Expired	1=Yes 2=No		
12	Others	1=Yes 2=No		
Outcome		Completed per protocol=1, Withdrawn=2, Lost to follow up =3		

Signature of the researcher:

Signature of the Guide/Co-guide

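### The adverse-effect checklist has no row for back pain or arthralgia, two reactions the protocol names for finerenone, so the safety profile cannot show them by type

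*Protocol*

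**What the plan says.** Section 5.11 G lists the expected reactions drug by drug.

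- Finerenone: "The most common adverse event of finerenone is hyperkalemia", followed by "Other common adverse events are decreased GFR, hypotension, back pain, dizziness, arthralgias, constipation".
- Dapagliflozin: "The most common adverse events of dapagliflozin is genital mycotic infection", followed by "Other adverse events are urinary tract infection, hypotension, hypoglycemia, acute kidney injury, DKA, Fournier's gangrene".

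Arthralgia appears again in section 5.11 F, item 5, as an example of a reason for withdrawal: "Drug intolerance or patient refusal to continue medication due to adverse effects like dizziness, arthralgia etc".

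Section 5.13 (evaluation at 4 weeks) states that "Safety will be evaluated based on the incidence of A/E" and that tolerability is judged from an adverse event profile. Section 5.10 carries adverse events as one categorical variable, "Present / Absent", reported as a frequency. Specific objective 5 (section 4.2) compares safety and tolerability profiles between the arms.

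Section 5.12 makes the case record form the data collection instrument. Its Adverse Effect table (Appendix) has 12 rows, each coded yes or no at 4 and 8 weeks. Ten rows name a reaction, one records death, and the last is *Others*, which is coded in the same way.

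**The concern.** Both arms receive dapagliflozin and only the experimental arm receives finerenone, so the reactions specific to finerenone are the ones the tolerability comparison most needs. The form asks by name about everything the protocol expects from the shared drug, but not about everything it expects from the added drug.

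A later analysis plan cannot repair this. If the form does not collect the type of an event, no analysis can recover it. What is at stake is the adverse event profile and specific objective 5. The primary outcome is not involved.

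**Working it through.** The protocol gives no figure on this point, so the check sets the two lists in section 5.11 G against the rows of the Adverse Effect table.

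| Reaction | Named for | Own row? | Other place in the records |
|---|---|---|---|
| Hyperkalaemia | finerenone | yes | serum potassium at each visit |
| Decreased GFR | finerenone | no | creatinine and eGFR at each visit; a row for acute kidney injury |
| Hypotension | both | yes | blood pressure |
| Back pain | finerenone | no | none by name |
| Dizziness | finerenone | yes | – |
| Arthralgia | finerenone | no | reason for withdrawal, only if the patient withdraws |
| Constipation | finerenone | yes | – |
| Genital mycotic infection | dapagliflozin | yes | swab culture if suspected |
| Urinary tract infection | dapagliflozin | yes | urine culture if suspected |
| Hypoglycaemia | dapagliflozin | yes | – |
| Acute kidney injury | dapagliflozin | yes | creatinine and eGFR at each visit |
| Diabetic ketoacidosis | dapagliflozin | yes | urine ketones and bicarbonate if suspected |
| Fournier's gangrene | dapagliflozin | yes | – |

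**Counts**

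- Distinct reactions: 7 + 7 − 1 shared (hypotension) = 13. Rows that name a reaction: 13 − 3 = 10, which agrees with the form.
- Dapagliflozin: 7 of 7 have a row.
- Finerenone: 7 − 3 = 4 of 7 have a row.
- Named for finerenone alone: 6 reactions, of which 3 (hyperkalaemia, dizziness, constipation) have a row.
- With decreased GFR credited to the eGFR values recorded at baseline, 4 and 8 weeks: 4 + 1 = 5 of 7. The two left over are back pain and arthralgia.

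**What the form returns if followed as printed.** Suppose one patient has both back pain and arthralgia at week 4, and another has a single unrelated complaint. Both are coded *Others* = yes.

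- Patients with any adverse event: 2, which is correct.
- Events by type: not available.
- Number of events: 2 recorded where there were 3.

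**After the fix.** With the two rows added, and decreased GFR derived from eGFR, finerenone coverage is 7 of 7. Dapagliflozin stays at 7 of 7.

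**Scale in patients (illustration only).** The protocol gives no rate for back pain or arthralgia. If each occurred in 5% of the 44 patients in the combination arm, 44 × 0.05 = 2.2 patients per event would lose their event type. Over an assumed range of 2% to 10%, this runs from 44 × 0.02 = 0.9 to 44 × 0.10 = 4.4. The conclusion does not depend on these rates.

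**The case against.** **A tick under *Others* is still an adverse event.** Section 5.10 defines a single present/absent variable, and section 5.13 judges safety by incidence. This stands for overall incidence. It does not answer section 5.13's adverse event profile, which needs event types.

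**Decreased GFR is well covered.** eGFR is recorded at every visit in both arms, and its change is specific objective 3. This stands in full and reduces the gap to two symptoms. Hyperkalaemia, the reaction named as most common for finerenone, is also well covered: it has its own row, serial potassium values and specific objective 2.

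**Other records exist.** The Data and Safety Monitoring Board appendix has a per-patient adverse event log with a comment column and a status table with a reason for withdrawal. These could hold the missing names. But the log has no column for the event itself, nothing requires the comment to name it, and the withdrawal reason catches only patients who leave.

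**The text of the form is imperfect.** Fill-in blanks and some column headings seem to have dropped out of the version at hand, so a line after *Others* may have been lost. This cannot be excluded. It bears on the *Others* item and not on the two absent rows.

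**A stronger inference is tempting.** A reader might conclude that finerenone's harms are under-counted and the comparison is biased towards no added harm. The documents do not support that. The same form serves both arms, and all patients are told to report any adverse event. In an open-label trial, knowing the allocation could raise unprompted reports in the combination arm as easily as lower them.

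**Conclusion.** The point holds as a gap in the form. Back pain and arthralgia, both named in the protocol for finerenone, are not prompted for and cannot be tabulated by type from the case record form. Several *other* events at one visit are recorded as one. Coverage by row is 7 of 7 for dapagliflozin against 4 of 7 for finerenone, or 5 of 7 once eGFR is credited.

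The consequence is limited to the adverse event profile and specific objective 5. Overall adverse-event incidence still includes any event ticked under *Others*. The primary UACR comparison and the potassium and eGFR comparisons are untouched. Neither a direction nor a size of bias can be stated.

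The conclusion assumes that the form is used as printed. The part about *Others* further assumes that no line for the event name was lost from the text at hand. If there is such a line, event types can be recovered from it, and what remains is that the two reactions are not prompted for.

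**What to change.** - Add rows for back pain and arthralgia to the Adverse Effect table, asked at weeks 4 and 8 in both arms.
- Change *Others* to *Others (name the event)*, with space for more than one entry.
- Tabulate these events by arm alongside the other listed events.
- Derive decreased GFR from the recorded eGFR. It needs no row that depends on judgement.

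The cost is two rows and one text field, with no extra visit, test or staff. The protocol calls the form pretested but does not say whether it is in use. If it is, a revised form has to be issued, and patients already seen may lack the new items.
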